### **Secondary Endpoint Objectives:**

- Objective improvements on sleep studies
  - Sleep breathing indices (AHI, RDI)
  - Sleep consolidation indices (SE%, REM%, REM min)
  - Objective Data Download (% compliance; % use, AHI, flattening %)
- Subjective Validated Psychometric Instruments
  - Sleep related impairment (ESS, VAS-F, VAS-S, III, FSS, SDB-6)
  - Quality of Life/Impairment (FOSQ-10, QLESQ, HSCL)

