### ***Synopsis***

Insomnia is the most common sleep disorder affecting millions of adults and is linked to daytime impairment. Insomnia is typically thought of as a symptom, secondary to a primary disorder, and often goes untreated for years. Medication (over the counter or prescription) and sleep hygiene are typical insomnia symptom treatments but they do not address the cause of the insomnia. Newer guidelines view insomnia as a co-morbid disorder needing independent treatment. Recent research has discovered high rates of sleep-disordered breathing (SDB) among insomnia patients; this co-morbid pairing is referred to as "complex insomnia." Several studies have revealed that treatment of SDB decreases insomnia.

This study will determine which of two different types of positive airway pressure (PAP therapy) modes are more effective in reducing sleep breathing events in chronic insomnia patients and in decreasing insomnia severity. Patients presenting to the clinic with a primary complaint of insomnia will be potential participants for this study. Following diagnostic polysomnography (PSG) testing, insomnia patients diagnosed with SDB and meeting inclusion criteria will be randomized to a PAP treatment arm, CPAP or ASV. No experimental devices will be used in this study, both CPAP and ASV are FDA approved for treatment of SDB and are in wide use in the USA. Participants will complete a series of three titration studies with their assigned PAP mode and attend a minimum of five clinical follow-up appointments over a 14-16 week timeframe. Titration PSG studies will assess PAP pressure needs to ensure that patients are receiving optimal therapy at all times during this study. Clinical follow-up visits occur every two weeks at which time objective data download information and subjective measures will be collected. PAP adaptation barriers will be addressed as they arise during the study, because it is important that participants are able to use PAP therapy nightly during participation in this protocol. Baseline scores on insomnia severity, sleep quality, subjective insomnia parameters, sleep related impairment, and quality of life will be compared to outcome measures at the 4 month mark. Pre-treatment and post-treatment objective improvements on sleep studies will also be compared including sleep breathing indices, sleep consolidation indices, and objective data download information.

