## Exclusion criteria:

1. Primary complaint of sleep-disordered breathing or issues with apneas during sleep
2. Severe respiratory disorder or severe sleep disorder such as restless leg syndrome (RLS), idiopathic hypersomnia, or narcolepsy
3. BMI  $> 30$  kg/m^2
4. Epworth Sleepiness Scale (ESS) score  $\geq 10$
5. Frequent napping behavior, such as a few times a week or more
6. Anticipated changes to start or stop sedative or psychotropic medications during the course of the trial.
7. Medical history of congestive heart failure (CHF) or other potentially unstable cardiac disease as well as chronic lung diseases or other debilitating medical conditions that manifest as more prominent in the patient's health compared to their sleep complaints.
8. Daily use of opiate medications
9. Known contraindications to PAP therapy as listed in the indication for use
10. Requires a CPAP (fixed) pressure  $> 20$  cm H2O
11. Inability to comply with study procedures

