#### **Questionnaires:**

**Insomnia Severity Index (ISI):** The seven-item questionnaire asks the individual to rate the level of insomnia and perceptions of sleep problems in the last two weeks. Answers must be provided using a scale from 0-4, with 0 reflecting no problem or being very satisfied to 4 indicating a very severe or very dissatisfied experience. Scores are divided into four tiers: 0-7 equates to no clinically significant insomnia, 8-14 equates to subthreshold insomnia, 15-21 indicates moderate severity insomnia, and 22-28 reflects severe insomnia.

**Epworth Sleepiness Scale (ESS):** The ESS is a simple, self-administered questionnaire which provides a measurement of an individual's general level of daytime sleepiness. The responder is asked on a scale of

0–3 to score the likelihood of falling asleep in eight various situations. A higher score indicates a higher level of sleepiness.

**Functional Outcomes of Sleep (FOSQ-10):** The FOSQ-10 is a shorter version of the FOSQ, an instrument used in both research and clinical practice to assess the impact daytime sleepiness has on daily living activities. Global scores range from 5 to 20; scores less than 15 indicative of severe impairment.

**Visual Analog Scale for Fatigue (VAS-F):** A single question on an 11 point Likert scale evaluating daytime fatigue. Higher scores are indicative of more fatigue.

**Visual Analog Scale for Sleepiness (VAS-S):** A single question on an 11 point Likert scale evaluating daytime sleepiness. Higher scores are indicative of more fatigue.

**Insomnia Impairment Index (III):** The III is an 11 item survey based on research diagnostic criteria for insomnia disorder, which measures forms of daytime impairment in relation to nighttime sleep difficulties. It uses a 5 –point Likert scale and is scored with an inter-item average (0 to 4), with higher scores denoting more impairment.

**Fatigue Severity Scale (FSS):** FSS is a 9 question survey on a 7 point Likert scale evaluating daytime fatigue. Higher scores are indicative of more fatigue.

**Sleep Disorder Breathing (SDB-6):** A 6 item survey assessing frequency (on a 4 point scale) and intensity (on a 4 point scale) of end organ symptoms of SDB including cognitive impairment, morning headache, dry mouth, and nocturia.

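### Entry is limited to ESS 0-9 and the screening score appears to be the baseline, so within-arm ESS change would drift upward by selection; the ASV versus CPAP comparison is not biased

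*Combined protocol and SAP*

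**What the plan says.** - **Entry rule.** Exclusion criterion 4 concerns the "Epworth Sleepiness Scale (ESS) score" and removes anyone at 10 or above. Criterion 5 also removes patients with "Frequent napping behavior, such as a few times a week or more".
- **Scale.** Under Questionnaires, the ESS asks the patient, on a scale of 0 to 3, "to score the likelihood of falling asleep in eight various situations". The total therefore runs from 0 to 24, higher meaning sleepier.
- **Endpoint.** Secondary Endpoint Objectives lists "Sleep related impairment (ESS, VAS-F, VAS-S, III, FSS, SDB-6" and, separately, "Quality of Life/Impairment (FOSQ-10, QLESQ, HSCL".
- **Comparison.** The Synopsis says: "Baseline scores on insomnia severity, sleep quality, subjective insomnia parameters, sleep related impairment, and quality of life will be compared to outcome measures" at the 4-month mark.
- **Analysis.** Data Analysis plans a repeated-measures ANOVA for the group-by-time interaction on the ISI, with effect sizes, and treats the other variables the same way. It does not say whether the effect sizes are between arms only.
- **Timing.** The questionnaires completed after consent and randomisation (Third Encounter) are a one-week diary, the III, the FSS and the Intake Supplement. ESS is not among them. It next appears at the follow-up visits, the first of which falls 10 to 14 days after device set-up.

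The documents do not state which ESS is the baseline, and they discuss neither restricted range nor regression to the mean.

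**The concern.** A patient admitted because one ESS reading was low will, on average, score higher on a second reading even if nothing has changed, since some low readings are low by measurement error. If that first reading is also the baseline, every baseline-to-exit ESS change carries an upward push unrelated to treatment. A patient entering at 9 can fall by at most 9 points and rise by as many as 15.

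Both arms receive PAP, so no untreated group would reveal the drift. The within-arm reading is a live one. The Background reports earlier PAP experience as pre-to-post ISI changes (16.8 to 9.7, d = 1.40; 19.0 to 11.9, d = 1.50), and the sample size is built from those effects. If ESS is reported in the same way, a real benefit could look small or absent, or sleepiness could seem to have worsened on PAP.

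**Working it through.** The plan contains no ESS mean, SD, reliability or expected change, so there is no figure of its own to reproduce. All distributional inputs below are assumptions.

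**1. Range (from the documents).** Maximum score 8 × 3 = 24. Admitted scores are 0 to 9, which is 10 of 25 possible values. The largest possible fall is 9; the largest rise from a score of 9 is 24 − 9 = 15.

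**2. Model.** Each observed ESS is a normal true score plus independent error, rounded and clipped to 0-24. Patients are kept if the first reading is 9 or less. The second reading has no treatment effect.

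**3. Approximate formula.** With retest correlation r, drift ≈ (1 − r) × (mean before exclusion − mean of those admitted).

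| Assumed mean, SD, r | Mean before / after exclusion | Formula | Simulated drift |
|---|---|---|---|
| 7, 4, 0.9 | 7.07 / 5.29 | 0.1 × 1.78 = 0.18 | 0.19 |
| 9, 5, 0.7 | 9.07 / 5.44 | 0.3 × 3.63 = 1.09 | 1.12 |
| 11, 5, 0.7 | 11.02 / 6.06 | 0.3 × 4.96 = 1.49 | 1.52 |

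The small gaps come from clipping at zero.

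**4. Range of drift.** Means of 5 to 6 with SD 4 to 4.5 give 0.1 to 0.5 points. Means of 7 to 11 with SD 4 to 5 give 0.2 to 1.5. The corner at mean 11, SD 5.5, r 0.7 gives 1.6. If a second ESS taken after eligibility serves as the baseline, the drift is 0.0 in every scenario.

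**5. Understatement of a real fall.** Suppose treatment lowers true scores by 30%.
- Mean 11, SD 5, r 0.7: admitted patients show a fall of 0.69. Measured against their own no-effect drift, the fall is 0.69 + 1.52 = 2.21.
- Mean 7, SD 4, r 0.9: the fall shown is 1.43, against 1.43 + 0.19 = 1.62.

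Across means 7 to 11 and SD 4 to 5, the fall shown is 0.7 to 1.7 points, against 2.1 to 3.3 in unselected patients. Part of that gap is a genuinely smaller effect in less sleepy patients; the rest is drift.

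**6. Between arms (mean 9, SD 4.5, r 0.8).**
- No effect in either arm: drift 0.67 and 0.66, difference 0.00.
- Additive effects (−2.5 on ASV, −1 on CPAP): d is 0.51 without the entry rule and 0.52 with it.
- Proportional effects (35% and 15%): the raw difference goes from 1.79 to 1.25, and d from 0.57 to 0.48.

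**7. Share at 10 or above at exit.** With no treatment effect, means of 7 to 11 and SD 4.5 to 5.5, 9% to 32% of admitted patients are at 10 or above on the second reading.

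**The case against.** The strongest reply is that the planned test is between arms. Selection acts before randomisation, so the drift is common to both groups and cancels in the group-by-time interaction. That stands. A reader might infer that the ASV versus CPAP result on ESS is biased; step 6 shows it is not.

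Second, the drift depends on the screening ESS being the baseline, which no section states. That also stands as a condition. The evidence is indirect: ESS is missing from the enrolment list and is next collected on treatment.

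Third, the size is assumed throughout. Patients must already have insomnia as their main complaint and not nap often, which plausibly lowers the mean before the ESS cut and pushes the drift towards 0.1 to 0.5 points. This is fair, and it is why the range starts at 0.1 and why the 1.6 corner should not be quoted alone.

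Fourth, the entry rule is not the main reason a null ESS contrast would be uninformative. At 25 per arm, power for the additive case is about 42% to 44% with or without the rule; for the proportional case it falls from 51% to 38%. Sample size is the main limit.

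What the reply does not remove is the Synopsis comparison with baseline, together with effect sizes whose type is left open.

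**Conclusion.** The point holds for within-arm ESS change, on condition that the screening score is the baseline. The bias is then upward, roughly 0.1 to 1.6 points under assumed pre-exclusion means of 5 to 11, SDs of 4 to 5.5 and retest correlations of 0.7 to 0.9. It is zero if ESS is re-measured after eligibility. It touches one secondary outcome; the ESS rule does not affect the primary ISI or bias the randomised comparison.

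Three stronger readings are not supported:
- **VAS-S and FOSQ-10 share the bias.** FOSQ-10 is described as "an instrument used in both research and clinical practice to assess the impact daytime sleepiness has on daily living activities", and VAS-S rates sleepiness, so both concern what the entry rule selects against. Neither is used for entry, neither is directly truncated, and the documents give no figure linking them to ESS. No bias is shown for them.
- **A null ESS result would count as a failed endpoint.** The plan sets no success rule or hierarchy for secondary outcomes.
- **ESS must leave the efficacy list.** The between-arm contrast remains valid, so dropping ESS or re-ranking its domain is a matter of preference.

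**What to change.** In Data Analysis:
- State which ESS is the baseline.
- Analyse ESS as a between-arm comparison of exit ESS adjusted for baseline ESS. In the scenarios tried, residual variance is a few percent lower than with change scores.
- Do not test or interpret within-arm ESS change, or its effect size, from the screening score.
- State that ESS is read in patients selected for low sleepiness.
- If the share at ESS 10 or above at exit is reported, compare it between arms only, because a sizeable share is expected from regression to the mean alone.

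This is a wording change on data already being collected. The downside is that no claim of within-arm ESS improvement can be made. If a within-arm description is wanted, an ESS repeated after eligibility and before PAP would remove the drift at the cost of one short questionnaire, but it would leave the limited room to fall.

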### **Other Tracking Variables**

- PAP Therapy Tracking Tools
  - PUDS, AEC, NOSE-8
- Change Tracking Tool
  - PGA (Insomnia, Sleep Quality, Fatigue, Sleepiness, Energy level)
  - Exit Interview

## **Subject Recruitment and Eligibility:**

All adult insomnia patients presenting at MSAS are potential candidates for this study. Potential participants are pre-screened to identify likely candidates. Medications need to be clarified and a discussion regarding possible upcoming medication changes/adjustments is necessary. The patients' travel plans for the next 3-6 months need to be discussed: length of trip, time zone changes, and dates of trip. Does the patient have computer access and will they be able and willing to complete daily 5min online tasks? Evaluate the patient's transportation situation and ability to return to the facility for follow up visits. Certain medical conditions or lifestyle habits may exclude patients from the protocol, including but not limited to: asthma, COPD, RLS, PLMD, smoking, epilepsy. Query mental or medical health problems and any upcoming procedures that may interfere with research protocol including surgery or elaborate testing that may affect sleep and decide if it is possible to work around these dates. Besides talk therapy, determine whether there are any plans for shock therapy or other brain stimulation that may affect sleep physiology. Have they recently started or do they plan to start insomnia treatment within the next few months (aside from coming to our sleep center for insomnia help)?

Participants who are currently treating their insomnia are eligible for the protocol as long as they maintain (or decrease/cease) the same treatment program throughout participation. Example: a patient taking sleep aids may continue to take sleep aids or decrease their dose but may not increase the dose or add another treatment, such as cognitive therapy, during involvement with this protocol.

**Inclusion and Exclusion Criteria:**

## Inclusion criteria:

1.  $\geq 18$  years old
2. Primary complaint of insomnia when presenting at clinic
3. Diagnosis of moderate to severe insomnia through the Insomnia Severity Index (ISI) with a score  $\geq 15$
4. Meet diagnostic criteria of Insomnia Disorder (per American Academy of Sleep Medicine)
5. Diagnosis of SDB, either OSA as determined by an AHI  $\geq 5$  events/hour or UARS with a RDI  $\geq 15$  events/hour and AHI  $< 5$  events/hour
6. Naïve to treatment for sleep-disordered breathing (SDB), including CPAP, APAP, ASV; mandibular repositioning devices (MRDs), and any other nasal or oral therapy with a primary indication of treating SDB
7. Able to fully understand study information in English and sign informed consent

## Exclusion criteria:

1. Primary complaint of sleep-disordered breathing or issues with apneas during sleep
2. Severe respiratory disorder or severe sleep disorder such as restless leg syndrome (RLS), idiopathic hypersomnia, or narcolepsy
3. BMI  $> 30$  kg/m^2
4. Epworth Sleepiness Scale (ESS) score  $\geq 10$
5. Frequent napping behavior, such as a few times a week or more
6. Anticipated changes to start or stop sedative or psychotropic medications during the course of the trial.
7. Medical history of congestive heart failure (CHF) or other potentially unstable cardiac disease as well as chronic lung diseases or other debilitating medical conditions that manifest as more prominent in the patient's health compared to their sleep complaints.
8. Daily use of opiate medications
9. Known contraindications to PAP therapy as listed in the indication for use
10. Requires a CPAP (fixed) pressure  $> 20$  cm H2O
11. Inability to comply with study procedures

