##### **Third Encounter (in person, at sleep lab)**

1. PSG results discussion with research coordinator
2. Confirmation that the patient meets I/E criteria
3. Patient reviews and signs informed consent form
4. [name] conducts airway exam and answers patient questions.
5. Subject randomized to treatment arm
6. Completion of special baseline questionnaires
  - a. One week Sleep Diary (see below) with Global Morning Rating of Nightly Sleep
  - b. Insomnia Impairment Index

- c. Fatigue Severity Scale
- d. Intake Supplement

7. Schedule Titration #1

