### **Special Considerations**

Due to the nature of this study and its short duration, it is necessary to expedite care of any issues that may be barriers to rapid acclimation of PAP. Without reasonably rapid acclimation, results will be skewed toward less than optimal outcomes for either treatment arm, therefore the items below will be addressed both prophylactically and as they arise.

1. Mask Issues
  - a. Common mask issues discussed with the patient during Set-up as well as trouble shooting for each problem.

- i. Mouth breathing or mouth leak
  - chinstrap will be demonstrated
- ii. Mask leak
  - Proper mask fit
  - Tightening the mask
  - Chinstrap
  - Mask liners (mask liners will also be recommended for soreness, mask creases, and pressure spots)

2. Aerophagia (air swallowing)
  - a. PAP therapy complication that can be very uncomfortable or even painful.
  - b. We would like all participants to be aware of aerophagia and bring this symptom to our attention immediately.
  - c. Leg jerks, mask issues, reflux, NAR, and pressure intolerance can all cause aerophagia and will require clinical attention.
3. Leg Jerks (sub-cohort potential)
  - a. Patients who did not report restless leg or periodic limb movement symptoms on their intake, but had significant leg movements during their diagnostic PSG (not respiratory related) will be excluded from the study if the leg jerks persist on the titration.
  - b. Patients who do not report leg movement symptoms on their intake and do not exhibit leg movements on their diagnostic PSG but do exhibit leg jerks on any titration study, will require careful re-evaluation of clinical care by [name] to determine if leg jerks are a separate co-morbid medical issue requiring withdrawal from the study.

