## **Research Rationale for Procedures**

### **Titration #1 (Initial)**

Participants return to MSAS sleep lab for a full night titration study during which only their assigned mode will be used. They will be fit with several masks and, with the help of a sleep technologist, will identify the best mask to start the PSG with and use during the study. The sleep technologist will titrate PAP pressure settings for each participant following AASM guidelines to eliminate all abnormal SDB wave forms, consolidate sleep, and achieve REM sleep with the assigned mode. All titrations will begin with low pressures, as recommended by the AASM, to help improve adaptation. Pressure settings will be determined to eliminate all SDB events (including RERAs). We anticipate that within the CPAP group the following trend will occur: aggressive treatment of RERAs will require increased pressure settings; these pressures will lead to expiratory pressure intolerance (EPI) or intolerance; and, “down” titration will be necessary for patient comfort. The highest pressures tolerated by the patient may not be equivalent to the pressures needed to effectively treat all SDB events. We would prefer to use pressures that treat all SDB events (including RERAs), but this may be an unrealistic goal for the CPAP group during the titration or the early adaptation period. Although we don’t anticipate as much of an issue of EPI or intolerance within the ASV group, we will follow the AASM procedure of “down” titration if it is needed. To avoid EPI and to help patients adapt to PAP, it may be

necessary to start CPAP patients on settings that do not treat all SDB events and increase settings over time. This approach may also occur with some ASV patients, but we expect the proportion of ASV patients with intolerance to be smaller than those using CPAP.

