### *Leg Jerks (sub cohort potential)*

Patients who did not report restless leg or periodic limb movement symptoms on their intake, but had significant leg movements during their PSG (not respiratory related) may be excluded from the study if they continue to show leg jerks on their titration study. Patients who do not report leg movement symptoms on their intake and do not exhibit leg movements on their diagnostic PSG but do exhibit leg jerks on any titration study, will require careful re-evaluation of clinical care by [name] to determine if leg jerks are a medical issue requiring withdrawal from the study.

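### Leg-jerk rules can remove patients after randomisation with no exit ISI required, and exclusion 10 can be judged only after randomisation and only in the CPAP arm

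*Combined protocol and SAP*

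**What the plan says.** **Order of events.** The Third Encounter lists "Confirmation that the patient meets I/E criteria" as step 2, "Subject randomized to treatment arm" as step 5 and the scheduling of Titration #1 as step 7. The Informed Consent section agrees that randomisation follows signature of the consent form. Titration #1 (Initial) is then a "full night titration study during which only their assigned mode will be used".

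**Leg jerks.** The rules appear twice and apply to both arms.
- *First branch:* no leg symptoms at intake, significant non-respiratory movements on the diagnostic PSG, and leg jerks again at titration. Special Considerations in the Study Procedure Summary says these patients "will be excluded from the study if the leg jerks persist on the titration". Leg Jerks (sub cohort potential), in the Research Rationale for Procedures, says they "may be excluded from the study if they continue to show leg jerks on their titration study".
- *Second branch:* patients with neither symptoms nor movements beforehand who "do exhibit leg jerks on any titration study" are re-evaluated by a clinician, who decides whether withdrawal is needed. The two sections agree on this branch.

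**Exclusion 10.** The criterion reads "Requires a CPAP (fixed) pressure" above 20 cm H2O. Inclusion item 6 requires patients to be naïve "to treatment for sleep-disordered breathing (SDB), including CPAP, APAP, ASV".

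**Analysis.** Data Analysis promises completer and ITT analyses. It does not define ITT, gives no rule for missing scores, and presents ITT as of limited relevance to an efficacy study.

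**The concern.** A patient taken out because of something found after randomisation leaves the comparison that randomisation set up. An ITT analysis protects against this only if outcomes are still collected. Here the final ISI belongs to an exit visit timed from the third titration, and the visible text describes no early-exit assessment. The removal rule is also stated once as mandatory and once as discretionary, so staff cannot follow both versions.

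Exclusion 10 raises a related problem. It is listed among the entry criteria but cannot be applied at entry. If staff treated it as an exclusion when the finding emerged, losses could arise in the CPAP arm only.

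**Working it through.** **1. When each finding can first be known**

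| Rule | Known at the eligibility check? | First observable | Arm |
|---|---|---|---|
| Leg jerks, first branch | In part: movements on the diagnostic PSG are known, persistence is not | At titration | Both |
| Leg jerks, second branch | No | Any titration, up to week 12 | Both |
| Exclusion 10 | No: no earlier PAP use, no titration yet | Titration #1 | CPAP only, since only the assigned mode is used |

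**2. ISI scores in hand at removal**

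Follow-up Appointments requires 2 retitration studies + 4 progress visits + 1 final visit = 7. Follow-up Visits and Titration #2 (Repeat) put the questionnaires at weeks 2, 4, 6, 8, 10 and 12 and at exit.

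- Removed after Titration #1: 0 of 7 post-baseline scores, because home treatment has not begun or has only just begun.
- Removed after Titration #2 (week 6): 3 of 7.
- Removed after Titration #3 (week 12): 6 of 7, with only the exit score missing.

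The primary test is a group-by-time interaction on the ISI. A patient with only a baseline score adds no information on change unless a rule for missing scores is stated.

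**3. Size**

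Inputs from Power Analysis and Sample Size: standardised difference 0.80, two-sided 0.05, 25 per group.

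The plan's own figure first. For 80% power, n per group = 2 × (1.960 + 0.842)² / 0.80² = 24.5, so 25 by the normal approximation (26 by the t-test). The planned 25 reproduces. At 25 v 25 the noncentral t gives 79.1% power. (The plan's 26 per group for 90% does not reproduce, but that is a separate matter and does not bear on this point.) The sample-size paragraph states no allowance for removals.

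The documents give no rate for either event, so the counts below are assumptions. Each patient is 1/25 = 4% of an arm.

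*Dropped from the analysis, effect unchanged at 0.80:*
- 24 v 25 (one removed, one arm only): 78.3%
- 24 v 24: 77.4%
- 23 v 23: 75.6%

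*Kept in the assigned arm, k patients per arm contributing no treatment contrast; effect = 0.80 × (25 − k)/25:*
- k = 1: 0.80 × 24/25 = 0.768, power 75.8%
- k = 2: 0.80 × 23/25 = 0.736, power 72.2%

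Keeping patients therefore costs 77.4 − 75.8 = 1.6 points at k = 1 and 75.6 − 72.2 = 3.4 points at k = 2, compared with dropping them. No bias figure is computed, because nothing in the documents says how removed patients would differ from those who stay.

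**The case against.** The strongest reply is that the plan already promises an ITT analysis, the events are likely to be few, and keeping the patients costs power.

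- *ITT is promised.* True. An undefined ITT with no rule for missing scores is also a general gap affecting every dropout. But these rules create missing outcomes by the plan's own instruction, and the promise does not help when no post-baseline ISI exists.
- *Few events.* This stands. RLS and PLMD are screened for before entry and BMI above 30 is excluded, so both events may be rare. The documents give no reason to expect leg-jerk removals to differ by arm.
- *Partly knowable beforehand.* This also stands for the first branch, which starts from the diagnostic PSG. The trigger for removal is still the titration.
- *Power.* The dilution is real. The case for keeping patients rests on preserving the randomised comparison, not on a gain in power.

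Three stronger readings are tempting and are not supported:

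- A reader might infer that exclusion 10 causes CPAP patients to be withdrawn. No visible text says so. The nearest guidance, in Titration #1 (Initial), concerns pressure intolerance and does not mention the 20 cm limit. It allows down-titration and settings that leave some events untreated, which points to staying in the arm at a lower pressure.
- A reader might suppose that such a patient stops PAP or moves to ASV during the trial, and calculate a shift in the contrast. Neither is described, and the other mode is offered only at the end of the study.
- A reader might take Final Dataset of RCT as an analysis-set rule that drops anyone outside weeks 14-16. In context it separates the trial data from the six-month clinical follow-up.

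The flow charts are not shown, so statements about absent handling apply to the visible text only.

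**Conclusion.** The concern holds in limited form. As written, the leg-jerk rules can remove randomised patients on post-randomisation findings. The two versions of the first branch conflict, and no exit ISI is required. The gap is widest after Titration #1, with 0 of 7 post-baseline scores, and narrow after Titration #3, with 6 of 7. Exclusion 10 cannot work as an entry criterion, and enforcing it later would remove patients from the CPAP arm only; the plan does not say that it would be enforced in that way.

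The direction and size of any bias are unknown and probably small. On the plan's 0.80 effect, losing one patient per arm lowers power from 79.1% to 77.4%. The number lost is an assumption. The point merits a change because the correction is cheap, not because a large distortion has been shown.

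**What to change.** 1. Make the two leg-jerk sections agree: leg jerks found after randomisation may change treatment but do not end follow-up.
2. State that exclusion 10 is not grounds for removal after randomisation. Such a patient stays in the CPAP arm at the highest tolerated pressure that the device can deliver, in line with the titration guidance already in the plan.
3. For both events, collect the ISI at weeks 14-16 and analyse the patient in the assigned arm in the ITT analysis. If the exit score is missing, use the interim two-weekly scores, and say what is done when only a baseline exists.
4. Report the number of each event by arm.

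The cost is protocol wording, a few extra questionnaires and slight dilution: 75.8% against 77.4% power with one patient per arm kept and not dropped, or 72.2% against 75.6% with two, if those patients contribute no treatment contrast.
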